Test Articles	TEST: Ingenol Mebutate Gel, 0.015% (Actavis) REFERENCE: Picato [®] (ingenol mebutate) Gel, 0.015% (LEO Pharma, Inc.) PLACEBO: Vehicle Gel (Actavis)
Study Objective	To evaluate the safety and therapeutic equivalence of generic ingenol mebutate gel, 0.015% to Picato gel, 0.015% by establishing the therapeutic comparability of the two active products and the superiority of the two active products over the vehicle gel in the treatment of actinic keratosis on the face and scalp.
Study Design	Multicenter, randomized, double-blind, vehicle-controlled, parallel group comparison.
Treatment Groups	Each enrolled subject will be randomized [REDACTED] to treatment with either generic ingenol mebutate gel, Picato Gel, or vehicle gel. Subjects will apply the test article to the Treatment Area once daily for three days.
Duration of Treatment	Three days.
Duration of Study	Approximately eight weeks for an individual subject.
Study Population	Male or female subjects at least 18 years of age with actinic keratosis (AKs) on the face or scalp. NOTE: Subjects may have AKs on both the face and scalp; however, only one contiguous skin area of approximately 25 cm ² (e.g., 5 cm x 5 cm) will be treated as part of this study.
Total Number of Subjects	Approximately 480 subjects [REDACTED]
Number of Sites	Approximately 26 sites will participate in the study.
Inclusion Criteria	To enter the study, a subject must meet the following criteria:

	
1. Subject is male or non-pregnant female 18 years of age or older.2. Females must be post-menopausal,¹ surgically sterile,² or use an effective method of birth control.^{3,4} Women of childbearing potential (WOCBP) must have a negative urine pregnancy test (UPT)⁵ at Visit 1/Baseline.3. Subject has provided written informed consent.4. Subject has a clinical diagnosis of AK at Visit 1/Baseline with at least four, but no more than eight visible and discrete non-hyperkeratotic, non-hypertrophic AK lesions, each at least 4 mm in diameter, within a contiguous 25 cm² treatment area ("the Treatment Area") located on the face or scalp.5. Subject is willing and able to apply the test article as directed, comply with study instructions, and commit to all follow-up visits for the duration of the study.6. Subject is in good general health and free of any disease state or physical condition that might impair evaluation of AK lesions or which, in the investigator's opinion, exposes the subject to an unacceptable risk by study participation.
Exclusion Criteria	
A subject is ineligible to enter the study if he/she meets one or more of the following criteria:
 
1. Subject is pregnant, lactating, or is planning to become pregnant during the study.2. Subject has a location of the selected contiguous 25 cm² Treatment Area that (a) is within 5 cm of an incompletely healed wound or (b) is in an area containing a lesion that was previously treated with ingenol mebutate.3. Subject has hyperkeratotic, hypertrophic, or large mat-like AKs (e.g., AK >1 cm² in size) within the contiguous 25 cm² Treatment Area.4. Subject has more than eight AKs, independent of size, within the selected contiguous 25 cm² Treatment Area.5. Subject has atopic dermatitis, basal cell carcinoma, eczema, psoriasis, rosacea, squamous cell carcinoma, xeroderma pigmentosum, or any other possibly confounding skin conditions on the region of the head that contains the Treatment Area (i.e., face or scalp).6. Subject has any skin pathology or condition that, in the investigator's opinion, could interfere with the evaluation of the test article or

¹ Defined as amenorrhea greater than 12 months in women 50 years of age and older.

² Hysterectomy, bilateral tubal ligation (at least six months prior to initiation of treatment), or bilateral oophorectomy.

³ Effective forms of birth control include a) hormonal contraceptives [e.g., oral, transdermal, injectable, or intravaginal], b) barrier methods [condom and spermicidal or diaphragm/cervical cap and spermicidal], c) partner vasectomy (performed at least six months prior to study entry), or d) total abstinence. Subjects who become sexually active or begin to have relations with a partner who is not sterile during the study must agree to use an effective form of birth control for the duration of the study.

⁴ WOCBP taking hormonal therapy must be on treatment prior to study entry and must not change their dosing regimen during the study; treatment must be for (1) oral or transdermal: at least one full cycle (e.g., four to eight weeks); (2) injectable (e.g., Depo-Provera) or intravaginal (e.g., intrauterine device [IUD]): at least one week; and continued per label.

⁵ UPT must have a minimum sensitivity of 25 mIU β -hCG/mL.

	
requires the use of interfering topical, systemic, or surgical therapy.
 
7. Subject is immunosuppressed (e.g., human immunodeficiency virus [HIV], systemic malignancy, graft host disease, etc.).8. Subject has experienced an unsuccessful outcome from previous ingenol mebutate therapy (an unsuccessful outcome is defined as after a reasonable therapeutic trial with no compliance issues and the topical drug did not work).9. Subject used topical creams, lotions, or gels of any kind within the selected Treatment Area within one day prior to entry into the study.10. Subject has the need or plans to be exposed to artificial tanning devices or excessive sunlight during the study or has used artificial tanners within two weeks of Visit 1/Baseline.11. Subject has used any of the following topical medications on the face or scalp:
• Corticosteroids within two weeks of Visit 1/Baseline;• Keratolytic-containing therapeutic products or medicated or irritant topical salves within two weeks of Visit 1/Baseline, including, but not limited to, alpha hydroxy acids (e.g., glycolic acid, lactic acid etc. >5%), beta hydroxy acid (salicylic acid >2%), and urea >5%;• Topical retinoids (e.g., tazarotene, adapalene, tretinoin) within two weeks of Visit 1/Baseline;• Light treatments (e.g., psoralen plus ultraviolet A [PUVA] therapy, UVB) within four weeks of Visit 1/Baseline;• Photodynamic therapy within eight weeks of Visit 1/Baseline;• 5-fluorouracil, diclofenac, imiquimod, or ingenol mebutate within eight weeks of Visit 1/Baseline; or• Other topical therapy for actinic keratosis within 2 cm of the selected contiguous 25 cm² Treatment Area within eight weeks of Visit 1/Baseline.12. Subject has had cryodestruction or chemodestruction, surgical excision, curettage, dermabrasion, chemical peel, or laser resurfacing on the Treatment Area (i.e. face or scalp) within two weeks prior to Visit 1/Baseline.13. Subject has used any of the following systemic medications:
• Corticosteroid therapy within one month;• Interferon/interferon inducers, cytotoxic drugs, immunomodulators, or immunosuppressive therapies within one month;• Retinoid therapy within six months prior to Visit 1/Baseline.14. Subject has lesions suspicious for skin cancer (skin cancer not ruled out by biopsy) or untreated skin cancers within the region of the head that contains the Treatment Area (i.e., face or scalp).15. Subject is currently enrolled in an investigational drug or device study.16. Subject has used an investigational drug or investigational device treatment within one month prior to Visit 1/Baseline.17. Subject has a history of sensitivity to any of the ingredients in the test articles (see Section 6.1).18. Subject has any condition which, in the investigator's opinion, would make it unsafe or preclude the subject's ability to fully participate in this research study.
--	---

	
19. Subject is unable to communicate or cooperate with the investigator due to language problems, poor mental development, impaired cerebral function or physical limitations.
 
20. Subject is known to be noncompliant or is unlikely to comply with the requirements of the study protocol (e.g., due to alcoholism, drug dependency, mental incapacity) in the opinion of the investigator.
 
21. Subject has been previously enrolled in the same study.

Study Procedures	
The study will consist of six clinic visits (see Schedule of Events). Subjects can be screened up to 30 days prior to Baseline for those subjects that are qualified for enrollment, but require wash-out of prohibited medications and/or therapies. Screening and Baseline may be combined into a single visit for those subjects who do not require washout. Subjects who require washout for longer than 30 days will be re-consented.
 
Visit 1 (Screening/Baseline): Day 1. The study requirements and procedures will be reviewed and written informed consent must be obtained prior to the initiation of any study-related procedures. Demographics, inclusion/exclusion criteria, medical/dermatological history, Fitzpatrick Skin Type assessment, and concomitant medications and therapies will be reviewed to determine subject eligibility. If required, the subject will be given adequate washout to discontinue prohibited medications or treatments as specified by the protocol.
 
Once washout has been completed, the following assessments will be performed. A brief physical exam including vital signs and UPT (if applicable) will be performed. The Treatment Area will be defined as a contiguous 25 cm² area on the face or scalp containing at least four, but no more than eight AKs. All AK lesions, independent of size, in the Treatment Area will be counted and evaluated for size. Local skin reactions (LSRs) will be assessed. Subject will be randomized (1:1:1) to treatment and instructed how to apply the test article to the Treatment Area via demonstration using non-medicated samples. Test article (with instructions) and subject diary will be dispensed to the subject. The subject will be instructed to apply the test article to the designated Treatment Area once per day for three days (washing their hands after each application) and to record the date and time of applications in the subject diary. After each application the test article will be washed off after six hours. The subject will be scheduled for follow-up at Visit 2/Day 4.
 
Visits 2, 3, and 4 (Follow-Up): Days 4, 8, and 15. The subject will return to the clinic and will be queried for any changes in health status and concomitant medications and therapies. The test article and subject diary will be collected at Day 4. LSRs will be assessed. The subject will be scheduled for the next follow-up visit.
 
Visit 5 (Follow-Up): Day 29. The subject will return to the clinic and will be queried for any changes in health status and concomitant medications and therapies. AK lesions, new and pre-existing (i.e., Baseline), will be counted. LSRs will be assessed. The subject will be scheduled for Visit 6/Day 57.
 
Visit 6 (End of Study [EOS]): Day 57. The subject will return to the clinic


Product Name: Generic Ingenol Mebutate Gel, 0.015%
Sponsor Name: Actavis Laboratories UT

Protocol: 094-8152-301
Protocol Date: May 26, 2016

	
and will be queried for any changes in health status and concomitant medications and therapies. A UPT (if applicable) will be performed. AK lesions, new and pre-existing (i.e., Baseline), will be counted. LSRs will be assessed. The subject will exit the study.

Study Measurements	
Efficacy: The primary clinical assessment is based on complete AK lesion clearance. The number of all visible and discrete non-hyperkeratotic, non-hypertrophic AK lesions (Baseline and new lesions) in the contiguous 25 cm² Treatment Area will be assessed by the investigator at Visit 1/Baseline, Visit 5/Day 29, and Visit 6/Day 57.
 
Safety: All adverse events (AEs) will be recorded. At each visit, the subject will be questioned specifically about any AEs associated with the application of the test article as well as the status of any ongoing AEs. In addition, LSRs will be assessed and UPTs (if applicable) will be performed per the Schedule of Events.
 
LSRs including erythema, flaking/scaling, crusting, swelling/edema, vesiculation/pustulation, erosion/ulceration, hyperpigmentation, hypopigmentation, and scarring will be assessed using a four-point ordinal scale where 0=absent, 1=mild (slight, barely perceptible), 2=moderate (distinct presence), and 3=severe (marked, intense). These LSRs will be collected independently of AEs. Only LSRs that require medical intervention (e.g., prescription medication), require withholding of the application of the test article), or extend beyond 2 cm outside of the Treatment Area will be documented as AEs. Any LSRs that are not listed above will be recorded as AEs.

Study Endpoints	
Efficacy Endpoints: Primary efficacy endpoint is the proportion of subjects in each treatment group with complete clearance of AK lesions. Complete clearance is defined as having no (zero) clinically visible AK lesions in the Treatment Area at Visit 6/Day 57.
 
Safety Endpoints:
 
• Incidence (including severity and causality) of any local and systemic treatment emergent AEs (TEAEs).• Incidence (by severity) of each individual LSR (erythema, flaking/scaling, crusting, swelling/edema, vesiculation/pustulation, erosion/ulceration, hyperpigmentation, hypopigmentation, and scarring) at Days 4, 8, 15, 29, and 57.
Sample Size Calculations	
Based on conservative assumptions of a complete lesion clearance rate of 50% for both active treatments and a rate of no more than 15% for the vehicle treatment, 480
 

Statistical Methods	
All statistical processing will be performed using SAS[®]. Summary tables (descriptive statistics and/or frequency tables) will be provided for baseline variables, efficacy variables, and safety variables. Continuous variables will be described by descriptive statistics (n, mean, median, standard deviation, minimum, and maximum). Frequency counts and percentage of subjects within each category will be provided for categorical data. Summaries will be provided for each treatment group.
 
Study Populations: The Safety population will include all randomized subjects who received the test article. The mITT population will include all randomized subjects who applied at least one dose of test article. The PP population will include all randomized subjects who met all the inclusion/exclusion criteria, were compliant with the assigned test articles (applied all three doses of the test article and no other evidence of material dosing noncompliance), completed the study within the designated visit window (± 2 days), and had no protocol violations that would affect treatment evaluation. Subjects who discontinued early from the study due to lack of treatment effect or who worsen and require alternate or supplemental therapy will be included in the PP population as treatment failures (non-responders). Subjects discontinued prematurely for other reasons will be excluded from the PP population, but included in the mITT population.
 
Efficacy Analyses: The efficacy analyses will be conducted on the mITT and PP populations. Last-observation-carried-forward (LOCF) will be used to impute missing values for efficacy variables in the mITT population.
 
Bioequivalence. Evaluations in the PP population will be considered primary. The 90% Wald's confidence interval with Yate's continuity correction will be constructed on the difference between the proportion of subjects with complete (100%) lesion clearance in the Test and Reference treatments to evaluate bioequivalence of the two active treatments. If the 90% confidence intervals on the difference between the proportion of subjects with complete lesion clearance in the Test and Reference treatments are contained within the interval -0.20 to +0.20, then the Test and Reference products will be considered to be therapeutically equivalent.
 
Superiority. To determine study sensitivity, two-sided, Fisher's exact test with an alpha of 0.05 will be used to evaluate the superiority of each active treatment over the vehicle for the proportion of subjects with complete (100%) lesion clearance using mITT population and LOCF. This test will be repeated on the PP population.
 
Safety Analyses: The analysis of safety will be conducted on the Safety population.
 
Dosing Compliance Descriptive statistics will be used to summarize test article compliance for the mITT and PP populations. Measures of test article compliance will include the total number of applications as determined from the data recorded in the subject diaries. Compliant subjects will be defined as those

----------------------------	---

	
who applied all three test article applications and had no other evidence of material dosing non-compliance.
 
Local Skin Reactions Severity of LSRs (erythema, flaking/scaling, crusting, swelling/edema, vesiculation/pustulation, erosion/ulceration, hyperpigmentation, hypopigmentation, and scarring) will be recorded. LSRs will be summarized for each treatment group by frequency and severity of each individual LSR at Baseline, and Days 4, 8, 15, 29, and 57. LSRs will also be summarized for each treatment group by the most intense score of each individual LSR and by the total score (sum of all LSRs) at Baseline, and Days 4, 8, 15, 29, and 57.
 
Adverse Events All AEs reported during the study will be listed, documenting course, severity, investigator assessment of the relationship to the test articles, and outcome. Verbatim terms on the electronic case report forms (eCRFs) will be linked to preferred terms (PTs) and system organ class (SOC) using the MedDRA mapping system. The PTs and SOC will then be tabulated. All reported AEs will be summarized by the number of subjects reporting AEs, SOC, PT, severity, and relationship to test article by treatment.

--	--

SCHEDULE OF EVENTS

VISIT	Visit 1 ⁶ Screening/ Baseline	Treatment Period (at home)	Visit 2 End of Treatment	Visit 3 Week 1	Visit 4 Week 2	Visit 5 Week 4	Visit 6 EOS ⁷ Week 8
DAY	1	1-3	4	8 ± 2	15 ± 2	29 ± 2	57 ± 2
Informed Consent	X						
Demographics	X						
Inclusion/Exclusion	X						
Medical / Dermatological History	X						
Fitzpatrick Skin Type Assessment	X						
Brief Physical Exam ⁸	X						
Vital Signs ⁹	X						
UPT ¹⁰ for WOCBP ¹¹	X						X
Definition of Treatment Area ¹²	X						
AK Lesion Count and Evaluation	X					X	X
LSR Assessment	X		X	X	X	X	X
Test Article Accountability: Dispense (D), Return (R)	D		R	R ¹³			
Subject Diary: Dispense (D), Return (R)	D		R	R ¹³			
Test Article Application		X					
Concomitant Medications and Therapies Review	X		X	X	X	X	X
Adverse Events	X		X	X	X	X	X

⁶ Screening assessments may be performed up to 30 days prior to Baseline for those subjects that are qualified for enrollment, but require wash-out of prohibited medications and/or therapies. Screening and Baseline may be combined into a single visit for those subjects who do not require washout. Subjects who require washout for longer than 30 days will be re-consented.

⁷ Or early discontinuation from the study.

⁸ Brief physical exam will include assessment of head and neck, cardiovascular, respiratory, gastrointestinal (abdomen), gross motor and gait.

⁹ Vital signs assessment will include height, weight, temperature, blood pressure (systolic and diastolic), heart rate, and respiration rate.

¹⁰ UPT must have minimum sensitivity of 25 mIU β-hCG/mL.

¹¹ WOCBP include any female who has experienced menarche and who has not undergone successful surgical sterilization (hysterectomy, bilateral tubal ligation, or bilateral oophorectomy) or is not postmenopausal [defined as amenorrheal >12 consecutive months in women 50 years of age and older].

¹² Treatment Area will be defined as a contiguous 25 cm² area on the face or scalp with at least four and no more than eight AKs.

¹³ Any “uncollected” test articles or subject diaries will be collected.

ABBREVIATIONS

AE	Adverse Event
AK	Actinic Keratosis or Keratoses
β-HCG	Beta-Human Chorionic Gonadotropin
cm	Centimeter
CFR	Code of Federal Regulations
CLIA	Clinical Laboratory Improvement Amendments
(e)CRF	(electronic) Case Report Form
EDC	Electronic Data Capture
EOS	End of Study
FDA	Food and Drug Administration
HIV	Human Immunodeficiency Virus
IRB	Institutional Review Board
IUD	Intrauterine Device
LOCF	Last Observation Carried Forward
LSR	Local Skin Reaction
MedDRA	Medical Dictionary for Regulatory Activities
mITT	Modified Intent-to-Treat
mL	Milliliter
OTC	Over-the-Counter
PP	Per-Protocol
PT	Preferred Term
PUVA	Psoralen + UltraViolet Light A
SAE	Serious Adverse Event
SAS	Statistical Analysis Software
SOC	System Organ Class
TEAE	Treatment Emergent Adverse Event
UPT	Urine Pregnancy Test
USP	United States Pharmacopeia
UVB	Ultraviolet Light B
WHO	World Health Organization
WOCBP	Women of Childbearing Potential

TABLE OF CONTENTS

Protocol Approval	2
Study Acknowledgement	3
Protocol Synopsis.....	4
Schedule of Events.....	11
Abbreviations	12
Table of Contents	13
1. Background	16
2. Rationale	16
3. Objective	17
4. Study Design	17
5. Study Population	17
5.1 Subject Eligibility	17
5.1.1 Inclusion Criteria	17
5.1.2 Exclusion Criteria	18
5.1.3 Subject Withdrawal Criteria	20
6. Test Articles and Regimen.....	20
6.1 Description	20
6.2 Instructions for Use and Application	20
6.3 Warnings, Precautions and Contraindications	21
7. Randomization Assignment	22
8. Prior and Concomitant Therapies	22
8.1 Prohibited Medications or Therapies	23
8.2 Allowed Medications or Therapies	23
9. Study Procedures	24
9.1 Visit 1 (Day 1): Screening/Baseline	24

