4. STUDY DESIGN

This is a multicenter, double-blind, vehicle-controlled, parallel group comparison study of a generic ingenol mebutate gel, 0.015% and Picato[®] (ingenol mebutate) gel, 0.015% (LEO Pharma, Inc.) in subjects 18 years of age and older with AKs on the face or scalp. Approximately 480 subjects will be enrolled at approximately 26 study sites.

Subjects will be randomized [REDACTED] to one of three treatment groups:

- **TEST:** Ingenol mebutate gel, 0.015% (Actavis)
- **REFERENCE:** Picato[®] (ingenol mebutate) gel, 0.015% (LEO Pharma Inc.)
- **PLACEBO:** Vehicle gel (Actavis)

Subjects will apply the test article to the designated Treatment Area once daily for three consecutive days. The Treatment Area will be defined as a contiguous 25 cm² area on the face or scalp with at least four, but no more than eight, visible and discrete non-hyperkeratotic, non-hypertrophic AK lesions, each at least 4 mm in diameter. Subjects will return to the clinic for follow-up on Days 4, 8, 15, 29, and 57. At the end of the study, safety and efficacy outcome measures will be compared to (a) determine if dosing with generic ingenol mebutate gel, 0.015% is therapeutically equivalent to the currently marketed Picato[®] (ingenol mebutate) gel, 0.015% and (b) both generic and reference active gel formulations are superior to the vehicle gel.

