7. RANDOMIZATION ASSIGNMENT

Subjects will be randomized to one of three treatments on a [REDACTED] basis (Test [generic gel, Actavis]: Reference [Picato[®] Gel, LEO Pharma, Inc.]: Placebo [vehicle gel, Actavis]). The study will use a block randomization scheme by investigational site, which reduces the probability of imbalance in treatment allocation [REDACTED] at any given time point. Subjects who are eligible for enrollment into the study will be randomized by assigning the lowest subject kit number available at the site. Treatment group designation will remain blinded until the final database is locked (unless unblinding is required, see Section 15).

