17. STATISTICAL CONSIDERATIONS

17.1 Sample Size

Based on conservative assumptions of a complete lesion clearance rate of 50% for both active treatments and a rate of no more than 15% for the vehicle treatment, 480 modified

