4 STUDY DESIGN

This is a multicenter, randomized, double-blind, vehicle-controlled, parallel group comparison study of a generic ingenol mebutate gel, 0.015% and Picato® (ingenol mebutate) gel, 0.015% (LEO Pharma, Inc.) in subjects 18 years of age and older with AKs on the face or scalp. Approximately 480 subjects with at least four (4), but no more than 8, visible and discrete nonhyperkeratotic, non-hypertrophic AK lesions, each at least 4 mm in diameter on the face or scalp who fulfill the inclusion/exclusion criteria will be enrolled at approximately 26 study sites.

Subjects will be randomized to one of three treatment groups on a [REDACTED] basis as follows:

- Ingenol mebutate gel, 0.015% (Actavis) [Test, generic]
- Picato® (ingenol mebutate) gel, 0.015% (LEO Pharma Inc.) [Reference]
- Vehicle gel (Actavis) [Placebo]

Subjects who are eligible for enrollment into the study will be randomized by assigning the lowest subject kit number available among kit numbers assigned by IWRS initially at each site. All subjects will apply the assigned test article to the designated Treatment Area once daily for three consecutive days. Subjects will return to the clinic for follow-up on Days 4, 8, 15, 29, and 57. At the end of the study, efficacy outcome measures will be compared to a) determine if dosing with generic ingenol mebutate gel, 0.015% is therapeutically equivalent to the currently marketed Picato® (ingenol mebutate) gel, 0.015% and b) both generic and reference active gel formulations are superior to the vehicle gel.

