8.9 Sample Size

8.10 Protocol Deviations

Protocol deviations will be provided in a subject listing.

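### Should the trial randomise fewer subjects to vehicle (3:3:2 or 2:2:1) to gain power for the equivalence test?

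*Protocol*

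**What the plan says.** The ratio can be read only in the Protocol Synopsis, Study Procedures, Visit 1: "Subject will be randomized (1:1:1) to treatment and instructed how to apply the test article". Elsewhere it is blacked out: Protocol Synopsis, Treatment Groups ("Each enrolled subject will be randomized [REDACTED] to treatment"), Protocol 4 ("Subjects will be randomized [REDACTED] to one of three treatment groups"), Protocol 7 ("Subjects will be randomized to one of three treatments on a [REDACTED] basis") and SAP 4 ("Subjects will be randomized to one of three treatment groups on a [REDACTED] basis as follows").

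Protocol 17.1 gives the planning rates: "Based on conservative assumptions of a complete lesion clearance rate of 50% for both active treatments and a rate of no more than 15" percent for vehicle. The visible text then stops at "for the vehicle treatment, 480 modified". SAP 8.9 shows only its heading, "8.9 Sample Size". Any target power, allowance for PP exclusions or reason for the arm sizes is therefore out of sight, which is not the same as absent.

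Equivalence is judged first in PP, by a 90% Wald interval with continuity correction lying within ±0.20 (Protocol 17.3.1, SAP 8.6.1). Protocol 17.3.1 adds that each active must also beat placebo at p < 0.05. Both documents run the superiority tests in the modified intent-to-treat (mITT) set and repeat them in PP; the SAP calls the PP repeat supportive. The protocol names Fisher's exact test. The SAP names a continuity-corrected chi-square test, with Fisher's test when an expected count is below 5.

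**The concern.** The comparisons differ greatly in difficulty at the planning rates. A 50% versus 15% contrast with 160 per arm is nearly impossible to miss, while two equal 50% arms inside ±0.20 leave a real chance of failure once PP exclusions are taken out. A third of the subjects therefore sit where they add almost nothing at the planned rates. Moving 40 of them (3:3:2, giving 180:180:120) or 64 (2:2:1, giving 192:192:96) to the active arms would raise equivalence power without enrolling anyone extra. If that gain were free, equal allocation would waste power on the trial's main question.

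**Working it through.** **Inputs.** 480 subjects; 50%/50%/15% clearance (Protocol 17.1); ±0.20 margin and 90% interval (Protocol 17.3.1). PP loss is not given in the readable text, so it is assumed at 0–30%, equal across arms, with the same clearance rates in PP and mITT.

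**The plan's own figure.** The 480 cannot be formally reproduced, because the target power and the allowance for losses are not readable. It is consistent with the usual two one-sided tests formula at 90% power without continuity correction: n per arm = 2p(1−p)(1.645 + 1.645)²/0.20² = 0.5 × 10.82/0.04 = 135.3, so 136. Three arms give 408, and 408/0.85 = 480. The 90% and the 15% are inferred, not stated.

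**Equivalence at the planned rates.** The half-width is 1.645·√(p₁(1−p₁)/n + p₂(1−p₂)/n) + 1/n, since the correction (1/n + 1/n)/2 equals 1/n for equal arms. With 136 per arm and observed rates near 50%, it is 0.0997 + 0.0074 = 0.107, so an observed difference up to about 0.093 passes. Enumerating all pairs of binomial outcomes gives the power:

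| Assumed PP loss | n per active arm (1:1:1 / 3:3:2 / 2:2:1) | 1:1:1 | 3:3:2 | 2:2:1 |
|---|---|---|---|---|
| 0% | 160 / 180 / 192 | 0.935 | 0.960 | 0.972 |
| 15% | 136 / 153 / 163 | 0.871 | 0.924 | 0.933 |
| 30% | 112 / 126 / 134 | 0.796 | 0.853 | 0.873 |

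At 15% loss the gains are 5.3 and 6.2 points. Exact power is saw-toothed in n. In 1-point steps of loss from 0 to 30%, the gains run from 2.5 to 7.5 points (3:3:2) and from 3.4 to 10.7 points (2:2:1).

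**Superiority at the planned rates.** With the SAP test in mITT, the chance of missing one comparison is 4.6 × 10⁻⁷, 2.4 × 10⁻⁶ and 1.4 × 10⁻⁵ for the three ratios. It is negligible in every case.

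**Joint success away from the planned rates.** Joint success means PP equivalence plus both superiority tests. The table uses the SAP test in PP at 15% loss, with vehicle arms of 136, 102 and 82:

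| Active / vehicle | 1:1:1 | 3:3:2 | 2:2:1 |
|---|---|---|---|
| 40% / 15% | 0.886 | 0.919 | 0.926 |
| 37% / 15% | 0.885 | 0.896 | 0.884 |
| 35% / 15% | 0.864 | 0.857 | 0.828 |
| 30% / 15% | 0.674 | 0.625 | 0.564 |
| 40% / 20% | 0.814 | 0.811 | 0.775 |

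With superiority in mITT instead, the 30%/15% row reads 0.756, 0.722 and 0.664. Equivalence power alone does not fall at low response: at 35% with no loss it is 0.954, 0.975 and 0.982. The superiority tests drive the decline.

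**Break-even.** With vehicle at 15% and the SAP test in PP, reallocation stops helping at about 35–36% active clearance for 3:3:2 and 37–38% for 2:2:1. These points are lower if superiority is required only in mITT, or if Fisher's test is used. With vehicle at 20%, both alternatives are already behind at 40% active clearance.

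**The case for a change.** The strongest case for reallocation is that the gain falls where the sponsor expects to be. The protocol calls its rates conservative. With vehicle at or below 15%, active response must fall about 12 points or more below plan before 2:2:1 loses. At 15% PP loss, 2:2:1 cuts the chance of failing equivalence from 12.9% to 6.7%. A vehicle rate below its ceiling makes reallocation safer: at 30% active and 10% vehicle, with superiority in mITT and 15% loss, joint success is 0.925, 0.943 and 0.935 for 1:1:1, 3:3:2 and 2:2:1. The 3:3:2 ratio keeps most of the gain with less exposure to low response. All of this stands as arithmetic.

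It does not settle the choice. The downside of 2:2:1 at 30% versus 15% is 9.2 points (mITT) or 11.0 points (PP), against 6.2 gained at plan. A vehicle rate above its assumed ceiling brings the losing region within 10 points of the planned active rate, and that is one of the risks a full-sized vehicle arm covers. Vehicle safety estimates also become less precise: the 95% half-width for a 15% event rate, 1.96·√(0.15 × 0.85/n), widens from 5.5 points to 6.4 (n = 120) or 7.1 (n = 96). A further 40 or 64 subjects would receive an active gel for which Protocol 6.3 warns of severe local skin reactions. A new ratio also needs a protocol amendment with IRB approval (Protocol 18.4) and a new randomisation list, and SAP 4 describes kit numbers already assigned to sites.

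A related worry is that the clause in Protocol 17.3.1 requiring both actives to beat placebo names no population. The superiority paragraph that follows it and SAP 8.6.1 both put those tests in mITT, with PP as a repeat, so an analyst has a clear reading.

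**Conclusion.** Equal allocation is a defensible trade-off and no change follows. At the planned rates and an assumed 15% PP loss, 3:3:2 or 2:2:1 would add 5.3 or 6.2 points of equivalence power. Joint success would be lower under both ratios if active response were near 30% with vehicle at 15%, or if vehicle reached 20% with active at 40%. The 1:1:1 design misses no figure stated in the documents: its equivalence power is 0.935 with no PP loss and about 0.80 at 30% loss. Whether more is wanted depends on the sponsor's power target and its appetite for protection against low response, and the readable text shows neither. These figures assume equal PP loss across arms and the same clearance rates in PP and mITT.
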